1.5 Randomization and Blinding

This study is a randomized, double-blinded, placebo-controlled, parallel-group Phase II study. Eligible study subjects are randomly assigned to HBM9036 or placebo group at a 1:1 ratio.

Subjects receive either HBM9036 Ophthalmic Solution (0.25%) or placebo solution as topical ophthalmic drops (at the ratio of 1:1) administered bilaterally BID. Subjects, Sponsor, CRO and site personnel are masked to treatment assignment.

2. General Analysis Definitions

2.1 Visit Windows

Subjects will be followed up for 8 weeks according to the study protocol. Table 2 summarizes planned office visits and analysis time window. Clinical assessments will be analyzed based on their study days when the assessments are performed, not based on the visit label in the database. Definition of visit time interval for the analysis purpose is provided in table 2.

Table 2. Summary of study visits according to the study protocol and this statistical analysis plan

Scheduled Visit	Timepoint label (Target day)	Scheduled Visit Window	Analysis Window*
Visit 1	Day-14	± 2 Days	Day -1 and before
Visit 2	Day 1	NA	Day 1
Visit 3	Day 8	± 1 Day	Day 2 to 12
Visit 4	Day 15	± 2 Days	Day 13 to 21
Visit 5	Day 29	± 2 Days	Day 22 to 42
Visit 6	Day 57	± 3 Days	Day 43 and after

*If there are more than 1 measure within the analysis window. The measure with the closest to the target day will be selected. If there are ties, the measure that are after the target day will be selected. If there are more than 1 measure on the same day, the average of these measures will be used. For descriptive result of endpoint like Abnormal or Normal, if there are more than 1 measure on the same day, and if the results are different, the Abnormal will be used.

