8.3 Unscheduled Visits and End of Treatment/Study Exit Visit

Repeat assessments, if needed, will be captured in unscheduled visits.

End of treatment/study exit visits will be captured as unscheduled visits. At least the following procedures will be completed at these visits:

- Record AEs and SAEs (if any);

- Review concomitant medications;
- Urine samples will be collected from women of childbearing potential for pregnancy tests;
- All the study drugs/subject diaries will be collected;
- Subjects will resume pre-study treatment or receive appropriate medication treatment;
- Subjects will be told to report all the SAEs that occur within 7 days after the last dose of study drug;
- Collect the reasons for discontinuation of study. These visits may be made to ensure safety of subjects. All the procedures performed at unscheduled visits must be recorded in the source documents and the eCRF page for unscheduled visits. For any procedure indicated in the eCRF, "unperformed" should be indicated if they have not been performed;
- Assessment that may be performed at unscheduled visits:
 1. Slit-lamp biomicroscopy;
 2. Visual acuity;
 3. Intraocular pressure;
 4. Urine pregnancy test;
 5. Fundus color photography or mydriasis fundus examination;
 6. Any other assessment needed in the judgement of the Investigator.

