9.5.2 Safety Analysis

Frequencies and percentages of subjects with treatment-emergent adverse events (TEAEs), serious TEAEs, and TEAEs causing premature discontinuation will be provided by treatment group. An AE is treatment emergent if it 1) occurs after the first dose of randomized study treatment or 2) if it is present prior to receipt of randomized study treatment but worsens in severity or increases in frequency after the first dose of randomized study treatment. Frequencies and percentages of subjects with AEs, SAEs, and AEs causing premature discontinuation will be provided by treatment group. The AEs will be listed by MedDRA SOCs and PTs and the AE listings will be categorized by severity, the causal relationship with study drug, and whether the AEs leading to discontinuation of study. No hypothesis test will be performed. Separate analyses will be performed for ocular specific and all AEs (including systemic).

Other safety endpoints including visual acuity, slit-lamp biomicroscopy, fundus color photography, drop tolerance, and intraocular pressure, will be summarized by treatment group and visit using descriptive statistics. Changes from baseline will also be summarized where appropriate. For assessments performed by eye, study eye and fellow eye will be summarized separately. In addition, shifts from baseline to worst on-treatment value will be summarized.

The exposure time (number of days) and drug administration times will be summarized by treatment group. The number and percentage of subjects with compliance will be calculated. The total exposure of the safety population will be summarized based on actual treatment received.

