7.2 Other Safety Endpoints

Best-Corrected Visual Acuity (ETDRS)

The observed and change from baseline visual acuity will be summarized for each eye (study eye and fellow eye) using continuous descriptive statistics by visit for each treatment group.

Slit-Lamp Biomicroscopy Examination

The results will be summarized using counts and percentages for each treatment group at each visit for each eye (study eye and fellow eye). Percentages will be based on the number of subjects in each treatment group with responses. Shift tables for the slit-lamp biomicroscopy parameters will also be provided comparing each follow-up visit to baseline.

Ora Calibra[®] Drop Comfort Assessment

Drop Comfort Questionnaire responses will be summarized by treatment group using qualitative summary statistics. Subjects with at least one negative response will also be

summarized by treatment group. Analyses will be performed on the SS.

Intraocular Pressure (IOP)

The IOP values and changes from baseline for each eye (study eye and fellow eye) will be summarized using continuous descriptive statistics by visit and eye for each treatment group and for all actively treated subjects.

Fundus photography/dilated fundoscopy

The following examinations are done in the study:

- Vitreous
- Retina
- Macula
- Choroid
- Optic Nerve

The results will be summarized using counts and percentages for each treatment group at each visit for each eye (study eye and fellow eye). Percentages will be based on the number of subjects in each treatment group with responses.

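### SAP 7.2 omits the protocol's baseline-to-worst-on-treatment shift, so an abnormal off-schedule slit-lamp or BCVA result can be superseded by a closer scheduled exam and no table recovers it

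*SAP*

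**What the plan says.** **Window rule.** SAP 2.1 states: "Clinical assessments will be analyzed based on their study days when the assessments are performed, not based on the visit label in the database". Its Table 2 gives the post-baseline windows as Days 2–12 (target 8), 13–21 (target 15), 22–42 (target 29) and, for Visit 6 (target 57), "Day 43 and after". If a window holds more than one measure, "The measure with the closest to the target day will be selected", and "If there are ties, the measure that are after the target day will be selected". For Normal/Abnormal results, priority goes to the abnormal one only within a day: "if there are more than 1 measure on the same day, and if the results are different, the Abnormal will be used". The rule is not limited to efficacy.

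**Off-schedule exams.** Protocol 8.3 records repeat assessments as unscheduled visits and adds: "End of treatment/study exit visits will be captured as unscheduled visits". Protocol Table 1 marks visual acuity, slit lamp, IOP and fundus photography at end of treatment. The text of 8.3 lists the same tests as ones that may be done at unscheduled visits.

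**Planned worst-value analysis.** Protocol 9.5.2, after describing by-visit summaries of the eye tests, says: "In addition, shifts from baseline to worst on-treatment value will be summarized". The synopsis repeats this and ties it to the ocular safety assessments.

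**What the SAP carries over.** For slit lamp, SAP 7.2 says: "Shift tables for the slit-lamp biomicroscopy parameters will also be provided comparing each follow-up visit to baseline". Fundus findings get counts and percentages by visit. BCVA and IOP get descriptive statistics by visit. No worst-value shift appears for any of the four, and no reason is given.

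**The concern.** Exams made off schedule are often made because something is wrong, or because the subject is leaving. A by-visit table that keeps one exam per window, chosen by calendar distance, can replace such an exam with a routine one. A worst-on-treatment shift is the usual safeguard, because it takes the most adverse value whatever its date. The protocol planned that safeguard. Protocol 9.10 says the SAP will describe all analyses in detail, yet SAP 7.2 leaves this one out.

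Ocular tolerability matters for this product. Protocol 1.4.2 reports 8 withdrawals for allergic conjunctivitis in the US study, 3 on 0.10% and 5 on 0.25%. SAP 1.4 also brings safety data into the phase 3 decision when the observed difference lies between -0.3 and -0.1. The eye-exam tables should therefore show the worst that was seen.

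**Working it through.** The plan states no figure on this point to reproduce. The check applies the SAP 2.1 rule day by day.

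**Inputs.** Windows and targets come from SAP Table 2. Permitted visit timing is ±1, ±2, ±2 and ±3 days for Visits 3 to 6 (SAP Table 2). Slit lamp and BCVA are done at every visit (Protocol Table 1). IOP and fundus are scheduled after baseline only at Visit 6 (Protocol 3.3), plus end of treatment (Table 1).

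**Rule.** Within a window with target T, keep the exam on day d with the smallest |d − T|; on a tie, keep the later one. Only non-visit days are counted, so the same-day rule does not come into play.

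**Slit lamp and BCVA, visits on Days 8, 15, 29 and 57.** One extra exam is placed on each non-visit day from Day 2 to Day 56:

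| Window | Extra exam before the visit | Extra exam after the visit |
|---|---|---|
| Visit 3 | Days 2–7 (6) | Days 9–12 (4) |
| Visit 4 | Days 13–14 (2) | Days 16–21 (6) |
| Visit 5 | Days 22–28 (7) | Days 30–42 (13) |
| Visit 6 | Days 43–56 (14) | – |

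Total days: 6 + 4 + 2 + 6 + 7 + 13 + 14 = 52.

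- *Early-exit exam, no later visit.* It competes only with a scheduled exam already done in the same window. Superseded: 4 + 6 + 13 = 23, and 23/52 = 44%. Kept: 6 + 2 + 7 + 14 = 29, and 29/52 = 56%.
- *Unscheduled exam, subject attends every visit.* Each window contains a scheduled exam at distance 0, so the extra exam always loses: 52/52 superseded.

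**Varying visit timing over every permitted combination.** Exit exams are kept on 53% to 67% of days, so superseded on 33% to 47%. Unscheduled exams in continuing subjects are kept on 0% to 27%, so superseded on 73% to 100%.

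**Example.** Visit 4 on Day 15 is normal and the exit slit lamp on Day 20 is abnormal. Both fall in Days 13–21. The distances are |15 − 15| = 0 and |20 − 15| = 5, so Day 15 is kept and the subject is tabulated as normal at Visit 4. Had the exit exam been on Day 14 with no later visit, it would have been the only exam in the window and kept.

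**IOP and fundus.** A single exit exam on any day is the only post-baseline measure in its window and is kept. A single unscheduled exam on Days 2–42 is also kept; one on Day 43 or later is superseded if Visit 6 is closer to Day 57. Exams kept before Day 43 appear in Visit 3 to 5 rows where none was scheduled. Because SAP 7.2 bases fundus percentages on subjects with responses, those rows describe essentially only subjects examined off schedule.

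**With the shift restored and all on-treatment exams feeding it,** an extra exam counts on 52 of 52 days.

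**The case against.** The strongest reply is that the eye-exam tables are not the main safety evidence. AE tables are not windowed. SAP 7 and 7.1 tabulate, by arm, TEAEs leading to discontinuation, withdrawals due to AEs, ocular TEAEs, treatment-related ocular TEAEs and maximal severity, and list all AEs. A withdrawal for allergic conjunctivitis would appear there in full. Assigning exams by study day also helps: it brings unscheduled and exit exams into the by-visit tables, and most exit days are kept. All of this stands. The AE route has one gap: Protocol 7.2.5 keeps signs attributed to fluctuation of dry eye, and expected signs triggered by the CAE, out of AE recording.

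A reader might infer that abnormal eye findings vanish from the safety reporting, or that the ocular safety comparison is biased toward no difference because the US withdrawals were all on active drug. The documents do not support either reading, for the reasons just given. Nor do they support turning 23/52 into a count of lost patients, such as about 2 of 5 withdrawals. That would need exits spread evenly over the days, an abnormal exit exam and a normal retained exam; the documents give no withdrawal timing.

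Two further limits stand. The protocol asks for the worst on-treatment value but does not say that unscheduled exams feed it, or whether an exit exam after the last dose counts as on-treatment. SAP section 1 also places table and listing samples in a separate document that is not available here. The omission is established for the SAP text only.

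**Conclusion.** The point holds for the eye-exam displays. A protocol-planned analysis is missing from SAP 7.2, and the selection rule in SAP 2.1 makes the omission matter for slit lamp and BCVA. Followed as written, the SAP can tabulate a subject with an abnormal off-schedule slit-lamp exam as normal for that window, or report the better of two BCVA values, with no worst-value table to show otherwise.

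The day shares in the working assume one extra exam per subject and scheduled visits within their permitted windows. They describe how the rule behaves, not how many subjects it will affect; that number depends on the timing and results of off-schedule exams, which the documents do not give. Effects on AE reporting and on the SAP 1.4 decision are not shown. This should be corrected, but it does not undermine the trial's safety assessment as a whole.

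**What to change.** 1. In SAP 2.1, state that the closest-to-target rule governs by-visit summaries only.
2. In SAP 7.2, restore the shift from baseline to worst on-treatment value for slit lamp, fundus, BCVA and IOP, by arm and by eye, on the Safety Set. State that scheduled, unscheduled and end-of-treatment exams all count, since the protocol leaves this open, and define the end of the on-treatment period for exit exams after the last dose.
3. Show the number of exams per arm beside the shift tables. Subjects with extra exams have more chances of an abnormal result, so an imbalance in exams could itself create a difference.
4. Add listings of all eye exams, if the separate table shells do not already contain them.

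The by-visit tables can stay as secondary displays. The cost is a few lines of SAP text and some extra tables and listings from data already collected.

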8.1.1 Visit 1: Day -13±2 to Subject Screening (CAE)

All subjects will be screened and assessed as follows.

Before entering the CAE

- Informed consent. Before change of drug treatment and/or invasive procedures (such as CAE), this study will be discussed with each subject, and those subjects who are willing to join this study must provide written informed consent.
- Demographics, medical/medication/ophthalmological history. All the demographic data, medical history, use of medications and underlying diseases will be collected and recorded. Only the serious non-ophthalmological medical history in the past one year and the medication history in the past 30 days are collected. The medications that subjects are receiving and have used but stopped within 30 days before screening will be recorded.
- Review of inclusion/exclusion criteria
- Urine pregnancy test (for females of childbearing potential). The result of urine pregnancy test for females of childbearing potential must be negative before participation in the study.
- Ora Calibra[®] Ocular Discomfort Scale
- Ora Calibra[®] Ocular Discomfort and 4-Symptom Questionnaire Ocular Discomfort Score
- Ocular discomforts assessed by Visual Analog Scale (VAS)
- OSDI[®]
- BCVA assessed by the ETDRS Charts. At Visit 1, the score for each eye of a subject must be 0.7 logMAR or better (Snellen equivalent score is 20/100 or better)
- Slit-lamp bio-microscopy. Slit-lamp bio-microscopy will be performed at the start of visit and be re-performed after CAE exposure to exclude any subjects with undesirable eye diseases.
- Conjunctival redness score. It is an objective index that assesses conjunctival redness through the Ora Calibra[®] Dry Eye Conjunctival Redness Scale. For an increment, half a point may be used (0.5 points).

- TFBUT
- Corneal staining (fluorescein), assessed by the Ora Calibra® Fluorescein Staining Rating Scale for cornea and conjunctiva
- AE query. All the AEs that occur after signing of ICF will be reported.

Screening Challenge (CAE # 1)

Subjects meeting all of the above evaluation (Pre-CAE® #1) criteria will undergo further screening evaluation in the CAE®. Subjects will be exposed to the CAE® for 90 ±5 minutes. Ocular discomfort self-assessment scores (ODS) will be obtained just prior to entering, during and just after the CAE® exposure. During the CAE® exposure, ODS will be collected at time 0 and every 5 minutes thereafter throughout the 90 ±5 minutes.

After leaving the CAE

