A maximum effort should be made to identify each number on the chart. When the subject says he or she cannot read a number, he or she should be encouraged to guess. If the subject identifies a number as 1 of 2 numbers, he or she should be asked to choose 1 number and, if necessary, to guess. When it becomes evident that no further meaningful readings can be made, despite encouragement to read or guess, the examiner should stop the test for that eye. However, all letters on the last line should be attempted as number difficulties vary and the last may be the only one read correctly. The targets missed or read incorrectly should be noted.

LogMAR Visual Acuity Calculations

The last line in which a number is read correctly will be taken as the base logMAR reading. To this value will be added the number "N x 0.02" where 'N' represents the total number of number targets missed up to and included in the last line read. This total sum represents the logMAR VA for that eye.

For Example: Subject correctly reads 4 of 5 numbers on the 0.2 line, and 2 of 5 numbers on the 0.1 line.

Base logMAR	= 0.1
N (total number of targets incorrect on line 0.2 as well as 0.1)	= 4
$N \times T$ (T=0.02)	= 0.08
Base logMAR + (N x T)	= 0.1 + 0.08
logMAR VA	= 0.18

Repeat the procedure for the left eye.

In order to provide standardized and well-controlled assessments of VA during the study, all VA assessments at a single site must be consistently done using the same lighting conditions and same correction if possible during the entire study. If the same correction cannot be used (ie, a subject forgets his glasses), the reason for the change in correction should be documented.

Slit Lamp Biomicroscopy Procedures

Slit lamp biomicroscopic observations will be graded as Normal or Abnormal. Abnormal findings will be categorized as clinically significant (findings that may interfere with study parameters or otherwise confound the data as determined by the investigator) or not clinically significant (NCS). The following will be examined:

- Cornea
- Conjunctiva
- Anterior Chamber
- Iris
- Lens
- Eyelid

External magnification and biomicroscopy will be performed using a slit-lamp. Magnification will be consistent with standard clinical practice. The subject will be seated.

Fundus Color Photography

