6.3 Secondary Efficacy Endpoints

Continuous and ordinal secondary efficacy variables collected at the specific visit will be summarized descriptively (n, mean, standard deviation, median, min and max). Change scores from pre- to post-CAE[®] will be calculated as post-CAE[®] – pre-CAE[®] score. The change from baseline will be calculated as visit – baseline. Two-sample t test and an ANCOVA model adjusting for baseline will also be assessed where appropriate. No imputation will be performed for secondary efficacy endpoints.

Tear film break-up time (TFBUT), conjunctival redness score, unanesthetized schirmer’s test result, ocular discomfort scale and visual analogue scale will be summarized by visit, time point, and treatment group using quantitative summary statistics. Changes from baseline will be compared between treatment groups using ANCOVA model that adjust for baseline. The differences in means, two-sided 95% confidence intervals (CIs) for the difference in means will be reported. Analyses will be performed on the PP population with observed data only.

Ocular discomfort and dry eye symptoms will be recorded by both visit and daily diary. For visit summary, quantitative summary statistics will be used as above. For diary summary, the average of the morning and evening assessments will be calculated for each day and symptom. Changes from baseline in weekly average scores at week 8 will be compared between treatment groups using ANCOVA model that adjust for baseline. The differences in means, two-sided 95% confidence intervals (CIs) for the difference in means will be reported. Analyses will be performed on the PP population with observed data only. Changes from baseline in weekly average scores of ocular discomfort, each individual symptom will be displayed graphically by week in a line plot by treatment group.

The OSDI[®] is assessed on a scale of 0 to 100, with higher scores representing greater disability.

The total OSDI[®] score is calculated by the following:

$$\text{OSDI}^{\circledR} = \frac{(\text{sum of scores}) \times 25}{\# \text{ of questions answered}}$$

Note that the number of questions answered in the denominator should exclude those questions with a response of “N/A”. Continuous descriptive statistics, including 95% CIs, as well as changes from baseline will be summarized by treatment group and visit.

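### The SAP's same-day rule does not separate pre-CAE from post-CAE slit-lamp exams, and its slit-lamp baseline, read literally, is a post-CAE exam at a different visit from the protocol's

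*SAP*

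**What the plan says.** **Schedule and grading.** Protocol Table 1 schedules slit-lamp before and after the CAE at Visits 1, 2, 5 and 6, and once at Visits 3 and 4, which have no CAE. Protocol 8.1.1 says the same for Visit 1: "Slit-lamp bio-microscopy will be performed at the start of visit and be re-performed after CAE exposure to exclude any subjects with undesirable eye diseases". Protocol Appendix 1 makes the result binary: "Slit lamp biomicroscopic observations will be graded as Normal or Abnormal". Abnormal findings are then classed as clinically significant or not.

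**Same-day rule.** The footnote to SAP Table 2 (section 2.1) has two parts. For numeric results: "If there are more than 1 measure on the same day, the average of these measures will be used". For Normal/Abnormal results: "if there are more than 1 measure on the same day, and if the results are different, the Abnormal will be used". Neither part mentions the CAE time point.

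**Tabulation.** SAP 7.2 reports slit-lamp by arm, visit and eye, with no time point, and adds: "Shift tables for the slit-lamp biomicroscopy parameters will also be provided comparing each follow-up visit to baseline". By contrast, SAP 6.3 says that break-up time, redness, Schirmer, ocular discomfort and VAS "will be summarized by visit, time point, and treatment group using quantitative summary statistics".

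**Baseline.** SAP 2.6 first gives a general rule of time-point matching for anything measured both pre- and post-CAE. It then gives slit-lamp, intraocular pressure and fundus examination a rule of their own: the final available value before the placebo run-in begins, normally at Visit 1. Protocol 9.4 has no such exception and uses the matched value at Visit 2.

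**The concern.** Fundus examination, the other Normal/Abnormal assessment, is scheduled once per visit. The only routine same-day pair on which the categorical rule can act is therefore the pre-CAE and post-CAE slit-lamp. Applied as written, the Visit 5 and Visit 6 tables would show the worse of a resting eye and an eye that has just had about 90 minutes of provocation. The Visit 3 and 4 tables would show a resting eye only, so the visits would not be comparable.

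The baseline adds a second difficulty. An eye recorded Abnormal at baseline because of the chamber cannot later show a Normal-to-Abnormal shift, whatever the drug does.

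This matters because ocular surface reactions are the known safety signal. The protocol's summary of earlier studies reports drug-related conjunctival hyperemia in 7 of 20 Phase I subjects. It also reports 8 withdrawals for allergic conjunctivitis in the US Phase II study, all on active drug and 5 of them at 0.25%. Under SAP 1.4, safety data also feed the decision when the primary result falls between −0.3 and −0.1.

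**Working it through.** The plan states no slit-lamp abnormality rate, so there is no figure to reproduce. The check has a textual part and an illustration of scale.

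**1. Does any other section keep the two exams apart?**

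- For staining, yes. SAP 6.2.1 defines the endpoint as post-CAE minus pre-CAE, so the averaging sentence cannot apply across time points.
- For the other graded signs and symptoms, yes. SAP 6.3 names the time point.
- For slit-lamp, no. SAP 7.2 stops at visit and eye.

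**2. Which exam is the slit-lamp baseline?** Protocol 8.1.1 places the first run-in placebo drop after the final post-CAE assessment at Visit 1. Both Visit 1 exams therefore precede run-in, and three readings are possible:

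- The last measure, taken literally: the post-CAE exam.
- The same-day rule applied first: Abnormal if either exam was Abnormal.
- The general matching rule still applying: one baseline per time point, but SAP 7.2 has no table that would use them.

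Under the first two, the baseline includes the effect of the chamber. Shifts to Visits 3 and 4 then compare a resting eye with a provoked one. A purely chamber-induced Abnormal at Visit 1 could also appear as an improvement in either arm.

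**3. Scale of dilution in counts.** Let p be the proportion Abnormal before the CAE, and c the share of otherwise normal eyes that turn Abnormal after it. Assume c is equal in both arms and independent of treatment.

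Merged proportion = 1 − (1 − p)(1 − c)

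Merged difference = (1 − c)(p_drug − p_placebo)

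The illustration uses n = 50 per arm (SAP 1.4) and assumed pre-CAE rates of 5% on placebo and 20% on drug:

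| c | Placebo | Drug | Expected Abnormal, placebo vs drug | Difference (points) | Share kept |
|---|---|---|---|---|---|
| 0 | 5.0% | 20.0% | 2.5 vs 10.0 | 15.0 | 100% |
| 0.1 | 14.5% | 28.0% | 7.25 vs 14.0 | 13.5 | 90% |
| 0.5 | 52.5% | 60.0% | 26.25 vs 30.0 | 7.5 | 50% |
| 0.9 | 90.5% | 92.0% | 45.25 vs 46.0 | 1.5 | 10% |

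The share kept is 1 − c whatever the assumed 5% and 20%.

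**4. Scale of masking in shift tables.** Assume that the chamber reaction recurs in the same subjects, that Visit 1 is post-CAE or merged, and that no eye is Abnormal before the CAE at baseline. The number per arm still able to show a new finding is 50 × (1 − c): 45 at c = 0.1, 25 at c = 0.5 and 5 at c = 0.9. With a 20% rate of new findings on drug, the visible shifts are 45 × 0.2 = 9, 25 × 0.2 = 5 and 5 × 0.2 = 1, against 50 × 0.2 = 10 with an undisturbed baseline.

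The values of c, 5% and 20% are all assumptions; the documents supply none of them.

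**The case against.** The strongest reply is that the merge is inferred and not instructed. The averaging sentence in the same footnote also lacks a time-point limit, and taken across time points it would make the primary endpoint impossible to compute. The author probably had repeat assessments in mind, which protocol 8.3 records as unscheduled visits. SAP 2.6 elsewhere treats pre- and post-CAE values as matched pairs, and table layouts sit in separate shells that are not part of the documents. All this shows that the rule is ambiguous. It does not supply a slit-lamp rule, and a programmer following SAP 2.1 and 7.2 would have no ground for splitting the exams.

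A reader might go further and infer that chamber-provoked findings will fill the safety tables and hide drug-caused ones. The documents do not support that, and the following points against it stand:

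- Subjects were selected on a rise in inferior fluorescein staining in the study eye. Slit-lamp is a separate judgement on six structures, listed before the staining assessment in the visit sequence. A staining rise does not establish an Abnormal slit-lamp grade, least of all in the fellow eye.
- Entry requires staining of at least 2 in a corneal subregion and redness of at least 1. Some resting eyes may therefore be Abnormal anyway, and separating the exams recovers nothing for those.
- Keeping Abnormal deletes no abnormal finding. Both arms undergo the same CAE, and Visit 3 and 4 counts are untouched.
- Ocular adverse events have their own tables and do not pass through this rule. Redness is graded separately and reported by time point.

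Two defences are only partial. Protocol 9.5.2 asks for shifts to the worst on-treatment value, which fits keeping Abnormal after baseline but does not call for a worst-case baseline. The adverse-event tables are not a complete backstop either: protocol 7.2.5 generally keeps dry eye fluctuation and CAE-triggered dry eye signs out of adverse-event reporting.

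**Conclusion.** The point holds as a gap in the analysis rules with a possible, unquantified effect on the slit-lamp tables. Read literally, SAP 2.1 with SAP 7.2 reduces two different exams to one at each CAE visit. SAP 2.6 points to a post-CAE baseline at Visit 1, in disagreement with protocol 9.4. Dilution and masking are real mechanisms. Their size depends on c, and the loss of a between-arm difference runs from 10% at c = 0.1 to 90% at c = 0.9, assuming the reaction is equal in both arms and independent of treatment. The documents do not show where in that range the trial lies, so a claim that drug effects will be hidden would go too far. Masking in the shift tables comes from SAP 2.6 as well as from the same-day rule, so amending the footnote alone would not be enough. The effect is confined to slit-lamp summaries, which are descriptive with no hypothesis test.

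**What to change.** 1. In the SAP 2.1 footnote, state that both same-day rules, averaging and keeping Abnormal, apply only to repeat measures within one CAE time point.
2. In SAP 7.2, tabulate slit-lamp counts and shifts separately: pre-CAE results together with Visits 3 and 4, and post-CAE results in a second table. Compare each with a time-point-matched baseline, using the pre-CAE baseline for Visits 3 and 4.
3. Reconcile SAP 2.6 with protocol 9.4 on which visit provides the slit-lamp baseline, and name the exam.

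The cost is a few lines of SAP wording and one additional table. Both exams are already scheduled, so no new data are needed.
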